***Illness Visits: Additional nasal swab specimens for the detection of RSV and respiratory pathogens" (including COVID-19) will also be collected from participants during illness visits and 48 hours later at any other protocol specified time point in the study (Table 5-4) including medically attended visits during RSV season. If a participant visits any other non-study doctor / hospital for a serious adverse event (SAE) at any time in the study, a nasal swab sample will be obtained at the study site once the participant is discharged, if deemed appropriate by the study investigator. All the nasal swab specimens will be collected in the recommended viral transport media tube and will be stored between -60°C and -80°C until ready to ship. The requirement for an onsite or at home illness visit will be evaluated first by video call to enable remote evaluation of severity and remote management of mild (Grade 1) illness, as deemed appropriate by the study investigator.

Table of Study Procedures for Cohorts 2 and 4 – Vaccination 1 (D0 to D55)

Phase I/II Study, 6 Planned Visits, 40 (42) Non-visit Telephone Contacts, 2 Vaccinations, 4 Planned Blood Samples, 2 Planned Nasal Swabs, up to a Maximum of 12 Months of Participation per Participant

Visit (V) / Contact	Visit 01	Phone contacts 1-6	Visit 02	Phone contacts 7-16	Phone contact 17	Phone contact 18	Illness Visit(s)‡ Visit 99
Study timelines – Days (D)	D0	Daily (x6)	D7	Three times weekly (x10) between D8 and D28	D29 (+1)	D42 (+1)	Any time between Visit 01 and Visit 06
In-person visit	X		X				X
Non-visit contact*		X		X	X	X	
Informed consent	X						
Demography data	X						
Inclusion / Exclusion criteria	X						
Medical history and physical examination	X						
Vital signs†	X		X				X
COVID-19 test	X						X
Interim history			X				X
Focused clinical examination			X				X
Collection of reportable concomitant medications/ vaccinations							X
Allocation of participant number	X						
Randomization / Dose number	X						
Blood samples	BL0001						
Nasal swabs‡			NS0001				NS0001 or UN0001 to UN0000X
Vaccination (1st administration)	X						
Immediate surveillance (30 min)§	X						

Visit (V) / Contact	Visit 01	Phone contacts 1-6	Visit 02	Phone contacts 7-16	Phone contact 17	Phone contact 18	Illness Visit(s) ‡ Visit 99
Study timelines – Days (D)	D0	Daily (x6)	D7	Three times weekly (x10) between D8 and D28	D29 (+1)	D42 (+1)	Any time between Visit 01 and Visit 06
Diary Card (DC) / electronic DC (eDC) provided	DC1/eDC		DC2				

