Phase I/II Study, 6 Planned Visits, 40 (42) Non-visit Telephone Contacts, 2 Vaccinations, 4 Planned Blood Samples, 2 Planned Nasal Swabs, up to a Maximum of 12 Months of Participation per Participant

Visit (V) / Contact	Visit 03	Phone contacts 19-24	Visit 04	Phone contacts 25-30	Visit 05 ^{†††}	Phone contact 31 – 40 (42) ^{‡‡}	Visit 06 ^{‡‡}	Illness Visit(s) *** Visit 99
Study timelines – Days (D)	D56+7	Daily (x6)	D63 (+7)	Twice weekly (x6) between D64 and D83	D84 (+8)	Every 2 weeks between Visit 05 and Visit 06	1 – 31 Oct (SH) 1 – 30 Apr (NH) or > 5 months after last vaccine admin.	Any time between Visit 01 and Visit 06
In-person visit	X		X		X		X	X
Non-visit contact*		X		X		X		
Vital signs [†]	X		X		X			X
Interim history	X		X		X			X
Focused clinical examination	X		X		X			X
COVID-19 test	X							X
Collection of reportable concomitant medications/ vaccinations	X							X
Dose Number	X							
Blood samples	BL0002				BL0003		BL00P2	
Nasal swabs [‡]			NS0002					NS0002 or UN0001 to UN000X
Vaccination (2nd administration)	X							
Immediate surveillance (30 min) [§]	X							
Diary Card (DC1)	DC3							
DC / eDC reviewed**	DC2/eDC	DC3/eDC **	DC3/eDC	DC3/eDC **	DC3/eDC		X	X
DC collected	DC1/DC2				DC3			

Visit (V) / Contact	Visit 03	Phone contacts 19-24	Visit 04	Phone contacts 25-30	Visit 05 ^{†††}	Phone contact 31 – 40 (42) ^{‡‡}	Visit 06 ^{‡‡}	Illness Visit(s) *** Visit 99
Study timelines – Days (D)	D56+7	Daily (x6)	D63 (+7)	Twice weekly (x6) between D64 and D83	D84 (+8)	Every 2 weeks between Visit 05 and Visit 06	1 – 31 Oct (SH) 1 – 30 Apr (NH) or > 5 months after last vaccine admin.	Any time between Visit 01 and Visit 06
Memory aid (MA) provided					X			
MA reviewed							X	X
Collection of solicited local respiratory and systemic reactions ^{††}	X	X	X	X	X			
Collection of unsolicited adverse events ^{††}	X	X	X	X	X			
Collection of adverse events of special interest ^{††}	X	X	X	X	X			
Collection of medical attended adverse events ^{††}	X	X	X	X	X			
Collection of serious adverse events					X			

*Non-site visit contacts are to be made by phone at scheduled timepoints in the study.

† Vital signs will be collected in the eCRF.

‡ All participants will provide a nasal swab sample for quantification of vaccine virus shedding at D63, i.e., 7 days after vaccination 2. The same nasal swab specimen will also be tested for respiratory pathogens (including COVID-19), if the participant is ill at the time of D63 visit.

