Progress has been made in the understanding of the RSV gene function (14), and the use of reverse genetic systems to engineer rationally designed attenuated RSV strains (15), including strains attenuated through deletion of the NS2 gene, like the current RSV Δ NS2/ Δ 1313/I1314L vaccine candidate. RSV NS2 is a virally encoded type I and III interferon antagonist that interferes with interferon induction and signaling (16) (17) (18). In chimpanzees, intranasal and intratracheal inoculation with a NS2 gene-deleted derivative of wild-type (wt) strain RSV-A2 resulted in reduced replication in the upper and lower respiratory tract compared to wt-RSV, and significant resistance to consequent challenge with wt RSV (19). Deletion of the NS2 or NS1 gene in bovine RSV (BRSV) led to increased interferon response to BRSV infection in calves (20). NS2 also functions as a pathogenicity factor, promoting epithelial cell shedding in vitro and in the hamster model (21) and its deletion may potentially reduce small airways obstruction improving the safety profile of such vaccine candidates. Deletion of the NS2 gene may be beneficial for vaccine safety, and the additional deletion of codon 1313 in the polymerase (L) gene, which also confers mild temperature sensitivity (shutoff temperature of 38°C–39°C [100.4°F–102.2°F]) for added safety (21). Substitution of leucine (L) for isoleucine (I) at codon 1314 further stabilizes the deletion of codon 1313 genetically and phenotypically. The level of attenuation, genetic stability and immunogenicity exhibited by the resultant RSV Δ NS2 Δ 1313/I1314L in nonhuman primates indicated that it was a promising candidate for evaluation in pediatric Phase I studies (22). Recently, safety and immunogenicity of RSV Δ NS2 Δ 1313/I1314L was evaluated in RSV seronegative children, 6–24 months of age. In this study, [REDACTED]

[REDACTED]. At the [REDACTED] dose, the vaccine candidate was highly attenuated and infectious for 80% of vaccine recipients. However, only 8 of 15 (53%) of vaccine recipients developed four-fold or greater increases in RSV-neutralizing serum antibodies. At the [REDACTED] dose, this candidate vaccine was shown to be well tolerated, infectious (resulted in successful infection in 100% of vaccinees) and immunogenic, inducing four-fold or greater

increases in RSV-neutralizing serum antibodies in 16 of 20 (80%) vaccine recipients (23), warranting further evaluation of this candidate as a vaccine for RSV.

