There are several published studies evaluating 2 or 3 administrations of attenuated RSV or parainfluenza virus type 3 (PIV3) candidate vaccines (5) (6) (9) (27) (28) (29) (30) (31) (32). Generally, there was a high level of restriction of the second administration, and limited serum immune responses. The main effect was vaccine infectivity in the individuals who did not respond to the first administration. Two administrations of RSV Δ NS2/ Δ 1313/I1314L may improve the infectivity of either dose.

Selection of vaccine dose using safety, infectivity, viral shedding and immunogenicity in infants and toddlers regardless of baseline RSV serostatus:

Given the plan for a future liquid formulation in which the targeted dose will decay over the shelf life of the product, the dose selection based on this study relates to the future clinical development with frozen product. The data will be analyzed for comparable safety, infectivity, and immunogenicity profile between the two doses utilized in this study to justify clinically the future dose range boundaries of the non-frozen liquid formulation for final commercialization. The vaccine dose for the frozen liquid product to be utilized in future late-stage studies is expected to be around mid-range of the planned operative range for the future liquid formulation of [REDACTED].

Therefore, an unblinded interim analysis for dose confirmation of RSV Δ NS2/ Δ 1313/I1314L vaccine is planned on participants from Cohorts 1, 2 and 3 and at least 90 participants enrolled in Cohort 4. The interim analysis will take place when participants have provided safety data up to the D84 timepoint and have D84 immunogenicity results available. Based on the results of this analysis, the dose for future clinical studies (frozen product) will be confirmed. The acceptability of safety, infectivity, and immunogenicity results of the two doses tested to justify clinically the future dose range boundaries of the non-frozen liquid formulation for final commercialization will also be descriptively assessed. The selected dose will then be confirmed during an early analysis.

An unblinded early analysis is planned on all participants when they have provided safety data up to the D84 timepoint and have D84 immunogenicity results available. Based on the results of this analysis, the dose for future studies will be confirmed.

Placebo group:

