Placebo recipients will be included in each cohort to establish the background rates of respiratory and febrile illnesses that occur in infants and toddlers.

Clinical hypothesis:

Both doses of the live-attenuated RSV Δ NS2/ Δ 1313/I1314L vaccine are anticipated to be safe and immunogenic in infants and toddlers. However, administration of either dose may be associated

with adverse events that become apparent only when analyzed in a larger number of participants than the numbers enrolled in Laboratory of Infectious Disease (LID)/ National Institute of Allergy and Infectious Diseases (NIAID)/NIH Phase Ia studies, where each study assessed 10 to 40 vaccinees. Additionally, the rate, magnitude and durability of antibody responses may differ according to dose, as well as the magnitude of the memory (anamnestic) seroresponse observed following naturally occurring RSV infection. The intranasal [REDACTED] device used in this study may also impact the safety and immunogenicity of the vaccine. Dose selection will be based on a descriptive comparison of the safety, infectivity and immunogenicity of 1 or 2 administrations of either dose category.

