The Acute Phase begins with vaccine administration on D0 and ends at midnight on the 28th day after vaccine administration (D28). The Acute Phase for the second vaccine administration begins on D56 post-vaccination and ends at midnight on D84

During the Acute Phase of the study, a study healthcare professional will be available by telephone 24 hours a day for consultation with parents / guardians / legally authorized representatives regarding any illnesses that may occur during this period. Study personnel will have daily contact with the parents / guardians / legally authorized representatives for the first 7 days after each vaccine administration and then 3 times weekly after Day 07 up to 28 days after each vaccine administration. This 28-day Acute Phase of safety follow-up is consistent with the duration of shedding of live-attenuated RSV viruses in RSV seronegative infants and toddlers (5) (6). If the parent / guardian/ legally authorized representative reports an SAE, a safety event that meets the study pause or stop criteria ([Section 5.1.6](#)), or symptoms suggestive of a respiratory tract illness, then an illness visit should be scheduled ([Section 5.1.4, Table 5-4](#)). During the Acute Phase, the eDC allows daily safety monitoring of the study participant and will be programmed to send an alert to the parent / guardian / legally authorized representative and study site when there are symptoms suggestive of respiratory tract illness ([Table 5-4](#)).

Post-Acute Phase:

The Post-Acute Phase for participants receiving 1 administration begins at 12:01am on D29 and ends at midnight on D56. The first Post-Acute Phase for participants receiving 2 administrations begins at 12:01am on D29 and ends at midnight on D56, except if second administration is exactly on D56 when it ends immediately before receipt of the second administration. The second Post-Acute Phase for participants receiving 2 administrations begins at 12:01am on D85 and ends at midnight on D112.

During the Post-Acute Phase of the study, parents / guardians / legally authorized representatives will be instructed to monitor for and contact study staff if their child has had symptoms that are suggestive of a serious adverse event. If the parent / guardian / legally authorized representative reports an SAE or safety event that meets the study pause or stop criteria ([Section 5.1.6](#)), then an illness visit should be scheduled ([Section 5.1.4, Table 5-4](#)).

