9.1.1.3.2 Reactogenicity (Solicited Reactions from Day 0 to Day 28 After Each Vaccination)

After each vaccination, the participant's parents / guardians / legally authorized representatives will be provided with a DC / eDC, and a digital thermometer, and will be instructed how to use them. The following items will be recorded by the participants in the diary card / electronic diary card on the day of vaccination and for the next 28 days (i.e., Day 0 through Day 28) until resolution:

- Daily temperature, with the route by which it was taken
- Daily measurement and intensity grade of any solicited administration site reactions (e.g., runny nose) and systemic reactions (e.g., fever)
- Action taken for each event (e.g., medication)

The action(s) taken by the parent / guardian / legally authorized representative to treat and/or manage any solicited reactions will be classified in the CRB using the following list (all applicable items should be checked):

- None
- Medication
- Health care provider contact
- Hospitalized
- Discontinuation of study vaccination

Parents / guardians / legally authorized representatives of study participants will be contacted by telephone each day for the first 7 days after each vaccination and then 3 times weekly after the D07 visit to remind them to record all safety information in the diary card / electronic diary card.

If the timing of the telephone call should fall on a weekend or a holiday, the call should be made on the next business day. If contact is not made on the designated day, study staff will continue calling until contact is made. Every telephone attempt and its outcome will be documented in the source document.

[Table 9-1](#) and [Table 9-2](#) present, respectively, the administration site reaction that is pre-listed in the diary cards and CRB, together with the intensity scales.

Table 9-1: Solicited administration site reactions: terminology, definitions, and intensity scales

CRB term (MedDRA lowest level term [LLT])	Rhinorrhea	Nasal congestion
Diary card term	Runny nose	Stuffy or blocked nose
Definition	
Two or more consecutive days of clear, mucous or purulent discharge from the nose.
 
Note: Not associated with crying, change of room temperature, or eating and drinking.
	
Two or more consecutive days of stuffy or blocked nose.
 
Note: Not associated with crying, change of room temperature, or eating or drinking.

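### After dose 2 the schedule gives two calls a week where Protocol Section 9 requires three, with no reason stated; the effect is probably small

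*Protocol*

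**What the plan says.** Two places in Protocol Section 9 set the contact frequency for the Acute Phase, and both apply it to every vaccination. Section 9.1.1.1 asks for daily contact in the first week and "then 3 times weekly after Day 07 up to 28 days after each vaccine administration". Section 9.1.1.3.2 says that parents are telephoned "each day for the first 7 days after each vaccination and then 3 times weekly after the D07 visit to remind them" to complete the diary.

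The procedures tables for Cohorts 2 and 4 follow this after dose 1 but not after dose 2. Contacts 7-16 in the Vaccination 1 table are "Three times weekly (x10) between D8 and D28", and a further call follows at D29. Contacts 25-30 in the Vaccination 2 table, and in SAP Table 3.3, are "Twice weekly (x6) between D64 and D83". Visit 05 follows at D84 (+8). Neither document explains the lower frequency.

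Three other statements bear on whether it matters:

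- On the length of the phase, 9.1.1.1 says: "This 28-day Acute Phase of safety follow-up is consistent with the duration of shedding of live-attenuated RSV viruses in RSV seronegative infants and toddlers".
- On second administrations in published studies, 5.1.2 says: "The main effect was vaccine infectivity in the individuals who did not respond to the first administration".
- On the use of the data, 5.1.2 says: "Dose selection will be based on a descriptive comparison of the safety, infectivity and immunogenicity of 1 or 2 administrations of either dose category".

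**The concern.** Section 9 and the tables give a site different instructions for the same three weeks, and it cannot follow both.

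The calls do more than prompt parents. Under 5.1.4.2 and 9.1.1.3, staff use them to go through the diary, ask about other events and decide whether an Illness Visit is needed. Most of the AESI definitions in 9.1.1.3.5 require a diagnosis by a medical professional. A sign that resolves before the site hears of it may therefore never be confirmed. AESIs within 28 days of each vaccination are a primary safety endpoint.

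If active contact is thinner after dose 2, short and mild illness could be picked up less often in that window than after dose 1. A lower dose-2 rate could then be read as better tolerability of the second administration, in a study that will compare one with two administrations. If some children are first infected by the vaccine at dose 2, that window is their first shedding period, and it has the lighter schedule.

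**Working it through.** **1. The scheduled count.** Contacts 25-30 are 6 calls. At two a week, D64 to D83 (20 days) gives 2 x 20/7 = 5.7, and D64 to D84 (21 days) gives 2 x 21/7 = 6.0. The table's x6 is reproduced. It is also built into the stated total for Cohorts 2 and 4: 6 + 10 + 1 + 1 + 6 + 6 + 10 (12) = 40 (42). So it is not a misprint in one cell.

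**2. The required count.** Three a week over D64 to D84 is 3 x 21/7 = 9 calls (8.6 over the 20 days to D83).

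**3. The shortfall.** 9 - 6 = 3 calls, or 3/9 = one third. Counting Visit 05 as a contact gives 7 against 9, still short. Visit 05 can count only towards 9.1.1.1, which speaks of contact; 9.1.1.3.2 asks for telephone calls. Mean spacing is 21/6 = 3.5 days as scheduled, against 21/9 = 2.3 days as required.

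**4. All scheduled contacts after each dose.**

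| | After dose 1 | After dose 2 |
|---|---|---|
| Daily calls, first week | 6 | 6 |
| Visit at day 7 | D7 | D63 |
| Calls from day 8 | 10 | 6 |
| Close of the Acute Phase | D29 call | D84 (+8) visit |
| Total | 16 calls + D29 call + 1 visit = 18 | 12 calls + 2 visits = 14 |

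Dose 2 has fewer calls but one more examination. After dose 1 no visit is scheduled between D7 and D56.

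**5. Who might be affected.** Section 5.1.2 reports that in earlier studies of other RSV and PIV3 candidates the second administration mainly infected children who had not responded to the first. Some children here may therefore have their first vaccine infection between D56 and D84. Serostatus is determined retrospectively (5.1.2). Infection is defined by laboratory shedding and titre results (9.2.2.1). Sites cannot pick these children out, so they receive the lighter schedule with everyone else. Restricted replication at dose 2 would support fewer calls only for children already infected at dose 1.

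**6. Which comparison is affected.** Within Cohort 2 and within Cohort 4, every arm has the same dose-2 schedule. Vaccine against placebo in the dose-2 window is therefore like with like. Dose 2 against dose 1 is not, because the schedules differ as in step 4.

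**The case against.** The strongest reply is that this is a wording conflict with little consequence. The eDC alerts the site to respiratory symptoms, and paper diaries are used only in certain cases. A study clinician can be reached by telephone at any hour in the Acute Phase. Parents are told at dose 2 to report any illness. Visit 05 includes a respiratory and EENT examination and a review of AESIs, which dose 1 lacks near day 28. Most of this stands, and it is why the likely loss is small. It does not reconcile the two instructions. An examination at D84 (+8) also cannot confirm a sign that came and went in the middle of the window.

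A second reply is that 5.1.2 describes strong restriction of second administrations and expects an anamnestic response after dose 2. That could be a reason for fewer calls, but the protocol does not give it as one, and it does not cover children who did not respond to dose 1.

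Stronger readings are tempting, and the documents do not support them:

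- *Dose 2 will be the first infection for a known number of children.* Section 1.1 says that at one redacted dose level "the vaccine candidate was highly attenuated and infectious for 80% of vaccine recipients". A reader might apply the remaining 20% to the 20 + 60 = 80 low-dose children given two doses and call the resulting 16 first infected at dose 2. That product is at most the number not infected at dose 1. It treats all 80 as RSV-naive, although 12.5 allows for 5% to 35% RSV-experienced. It also assumes that this low dose, given with a different device, infects at the same rate. Section 5.1.2 says only that two administrations may improve infectivity.
- *A stated number of AESIs or LRIs will be missed.* That needs the duration of signs, the illness rate and the share of illnesses that only a call would reveal. The documents give none of these.
- *The vaccine-placebo safety comparison is biased by unequal follow-up.* Calls are equal across randomized arms.

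**Conclusion.** The inconsistency stands and lies in current operative text: about 9 calls required after dose 2 and 6 scheduled, or 7 contacts against 9 with Visit 05. Dose 1 receives 10 calls and a D29 call. The counts rest only on the tables and on a 21-day window.

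The consequence is likely small and cannot be quantified from the documents. It bears mainly on comparing event rates after dose 2 with those after dose 1. That some children are first infected by the vaccine at dose 2 is plausible from 5.1.2, but it is inferred from other candidates and their number is unknown. This is a point to consider, worth correcting because the remedy is cheap and Section 9 already requires it.

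**What to change.** For any second doses still to be given, change the dose-2 row to three times weekly (x9, D64 to D83) in the Protocol Vaccination 2 table and in SAP Table 3.3. The calls become contacts 25-33, the surveillance calls 34-43 (45), and the total 40 + 3 = 43 (42 + 3 = 45). Section 9 then needs no edit. If twice weekly is kept on purpose, give the reason in 5.1.2 and amend both Section 9 sentences; that removes the contradiction but leaves the two dose windows uneven.

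On the approximate calendar in 5.1.5, most or all second doses may already have been given. For those, read dose-2 AESI rates against placebo in the same window, and do not take a dose-2 rate below the dose-1 rate as evidence of better tolerability. SAP 5.1.1.2 already plans AESIs by vaccine group after each vaccination, so no new analysis is needed.

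If the study report describes contact intensity, give all scheduled contacts: after dose 1, 16 calls plus the D29 call and the D7 visit; after dose 2, 12 calls plus the D63 and D84 visits. Call counts alone would hide the extra examination after dose 2.

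Cost: three calls for each remaining second-dose child and one row in two tables. No new visits or samples.
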